6.6 HANDLING OF MISSING DATA AND OUTLIERS

Every reasonable attempt will be undertaken to ensure completeness of data collection. In general, missing data will be treated as missing. Imputation will be permitted, if deemed appropriate and on a case-by-case basis, depending on the extent and distribution of missing values.

The percentage of and reason for discontinuation from treatment and study follow-up will be summarized overall in Cohort A, by treatment in Cohort B, and by other relevant factors. In addition, if the proportion of discontinued patients is substantial enough (e.g. $\geq 10\%$) to warrant further investigation, baseline characteristics will be described for patients who discontinued prematurely in comparison to patients who have completed the treatment or study follow-up up to Visit 3.

As to PACT-Q2, the convenience and satisfaction dimension scores are calculated separately only if at least 50% of items of the dimension are completed for a patient at a visit. [\(3\)](#) See [Section 7.6](#) for imputation details when at least 50% of items of a dimension are completed.

The amount of missing data will be described and assessed in the report based on the descriptive summary tables by topic (category 'Missing' will be displayed if missing occurs in the data).

Missing or incomplete ADR or fatal AE dates are imputed according to BI standards (see “Handling of missing and incomplete AE dates”) [\(4\)](#).

6.7 BASELINE, TIME WINDOWS AND CALCULATED VISITS

The baseline visit is defined as the physical visit where the patient is enrolled in the registry. Baseline values are the values collected at baseline visit (Visit 1).

Patients will be followed over an observation period of 6 months. Data will be collected at three time points:

1. At Baseline (initiation on Pradaxa[®] or VKA)
2. 30-45 days after initiation on Pradaxa[®] or VKA (initiation period)
3. 150-210 days after initiation on Pradaxa[®] or VKA (continuation period)

As indicated in [Section 6.1](#), Visit 2 data that were collected between 7 and 124 days after baseline will be included for analysis; Visit 3 data that were collected between 125 and 365 days after baseline will be included for analysis.

7. PLANNED ANALYSIS

For End-Of-Text (EoT) tables, the set of summary statistics is: N / Mean / SD / Min / Median / Max.

Tabulations of frequencies for categorical data will include all possible categories and will display the number of observations in a category as well as the percentage (%) relative to the respective treatment group (unless otherwise specified, all patients in the respective patient set whether they have non-missing values or not). Percentages will be rounded to one decimal place. The category missing will be displayed only if there are actually missing values.

The summary of data will be done by cohort and by treatment (Pradaxa[®] or VKA) within Cohort B.

7.1 DEMOGRAPHIC AND OTHER BASELINE CHARACTERISTICS

Analysis of demographic and other baseline characteristics is defined as a main analysis for Objective 2. Details regarding the main analysis can be found in [Section 7.6](#).

7.2 CONCOMITANT DISEASES AND MEDICATION

Only the information on the pre-specified medical history/concomitant diseases and pre-specified concomitant therapies is collected in the eCRF.

The pre-specified diseases in the past and those while on treatment will be summarized by pre-specified category and condition / diagnosis.

The pre-specified therapies have already been named in accordance with the WHO Drug coding dictionary. The pre-specified therapies taken in the past and those taken concomitantly while on treatment will be summarized by pre-specified term. Analysis of concomitant diseases and concomitant therapies at the time of baseline visit is defined as a main analysis for Objective 2. Details regarding the main analysis can be found in Section 7.6.

7.3 TREATMENT ADHERENCE

Not applicable for this study. Treatment adherence is not assessed in this study.

7.4 METHODS ADDRESSING BIAS

See registry protocol Section 9.9.

7.5 METHODS ADDRESSING CONFOUNDING/EFFECT MEASURE MODIFICATION

Propensity score matching will be used to correct for identified confounders. However unidentified confounders cannot be controlled for using statistical analysis. For details on the propensity score matching method, see Section 7.6.

7.6 MAIN ANALYSES

Due to the nature of this non-interventional study, there is no (confirmatory) hypothesis testing foreseen in a strict statistical sense. Analyses are descriptive in nature and confidence intervals and p-values from statistical models are used for exploratory purposes.

For the PACT-Q1, no global score is calculated as each item is analysed individually (3).

Within the PACT-Q2, items for convenience and for burden of disease and treatment are reversed (reversed score = 6 – item score), added together and rescaled on a 0-100 scale to obtain the convenience dimension score. Items for anticoagulant treatment satisfaction are summed and rescaled on a 0-100 scale to determine the satisfaction dimension score (3).

The convenience and satisfaction scores are calculated separately only if at least 50% of items of the dimension for a patient at a visit are completed. For convenience and satisfaction dimension scores, if at least 50% of items are completed (non-missing) for a dimension, the missing items of a patient at a visit are replaced by the mean of non-missing items of the dimension obtained at the same visit for the same patient. Then sums of items of dimensions are calculated and rescaled on a 0-100 scale as follow (3):

$$\text{Score} = 100 \times (\text{sum} - \text{minimal possible sum}) / (\text{highest possible sum} - \text{minimal possible sum})$$

The PACT-Q1 scores which were collected after first dose, the PACT-Q2 scores which were collected more than 1 day after patients discontinued from the treatment, and the PACT-Q scores which were collected using incorrect PACT-Q procedure will be excluded from the summaries or analyses.

For Cohort A, the mean convenience and satisfaction dimension scores of PACT-Q2 at the second assessment (Visit 2) and last assessment (Visit 3) will be compared with the baseline assessment (Visit 1) using paired t-tests.

For Cohort B, mean Convenience and Satisfaction dimension scores of PACT-Q2 will be compared between Pradaxa[®] and VKA patients at the second and last assessments. Given the nature of this non-interventional study, patient in the two treatment groups may differ with regard to important baseline demographics and disease characteristics. Therefore, a preliminary assessment of the comparability of the Pradaxa[®] and VKA patients based on propensity scores will be performed when approximately half of the target sample size is reached. As a first step of the assessment, propensity scores that estimate the probabilities that patients would be initiated on Pradaxa[®] will be calculated using a logistic regression model as specified below:

- Dependent variable in the propensity score model is treatment choice (Pradaxa[®] or VKA).
- The following baseline variables that are either potential confounders (associated with both treatment choice and outcome) or potential predictors of outcome will be included as covariates.
 - Age at baseline (< 65, ≥ 65 and < 75, ≥ 75 years)
 - Gender (male, female)
 - Pooled country (South Korea, non-South Korea)

- Creatinine clearance at baseline (<30 and 30 to < 50 combined, 50 to < 80, ≥ 80 mL/min, not available)
 - CHA₂DS₂-VASc stroke risk score at baseline (low risk [score of 0], intermediate risk [score of 1], high risk [score of ≥ 2])
 - HAS-BLED bleeding risk score at baseline (low risk [score of < 3], high risk [score of ≥ 3])
 - Co-morbidities – group 1 (malignancy, no malignancy)
 - Co-morbidities – group 2 (ulcerative GI disease or gastritis, no ulcerative GI disease or gastritis)
 - Concomitant therapies – group 1 (verapamil, amiodarone, and dronedarone, vs. no p-gp-inhibitors)
 - Concomitant therapies – group 2 (any antithrombotic agent, no antithrombotic agent)
 - Concomitant therapies – group 3 (NSAIDS, no NSAIDS)
 - Type of physician (cardiologist, non-cardiologist)
 - Type of hospital or practice (Public and other combined, private)
 - Owner of medical practice (Physician or physician group, medical / academic health center, others)
- If a variable is suitable but has a high number of missing values, further discussion will be carried out to decide whether it will be excluded from the propensity score model or still be included in the propensity score model with missing as a separate category.
 - Variable selection will be performed with caution to avoid the inclusion of highly correlated variables as well as over-parameterization.
 - All covariates from the list above will be set as required covariates in the propensity score model to ensure balance of baseline characteristics of patients. If any additional covariates are deemed necessary to be included in the propensity score model, they need to be defined before database lock.

Pradaxa[®] and VKA patients will then be matched based on propensity scores using a variable ratio, parallel, balanced 1:n, nearest neighbour matching algorithm with a caliper width of 0.05 and without replacement. The publicly available SAS macro provided by Rassen et al. (5) will be used.

Finally, the percentage of Pradaxa[®] and VKA patients that are matched with an appropriate maximum ratio (e.g. 2:1) according to the actual patient distribution will be calculated to assess the comparability of the two patient populations, and to estimate the loss of patients from the comparative analysis.

For the final comparative analysis for Cohort B, Pradaxa[®] and VKA patients will be matched based on propensity scores following the same approach as described above. To assess the performance of the propensity score matching procedure, patient demographics and disease characteristics at baseline will be descriptively summarized again for the matched patients by treatment. For each matched set that includes multiple Pradaxa patients, the mean PACT-Q2 score will be calculated for the Pradaxa patients and used in the final comparative analysis. Finally, the mean PACT-Q2 scores at each of the second and last assessments will be compared between the matched Pradaxa[®] and VKA patients using paired t-tests.

For both cohorts, the primary analyses will be based on the actual anticoagulation treatment the patients receive (i.e. “as treated” analysis). A patient is considered to have permanently discontinued initial anticoagulation treatment if other relevant anticoagulation treatment is initiated or otherwise dependent on the duration of treatment interruption. Whether a patient discontinued from the Pradaxa[®] or VKA is recorded on the eCRF. Patients who have permanently discontinued initial anticoagulation treatment at the time of an assessment will be excluded from all analyses where data from that assessment is included.

Patient demographics and disease characteristics at baseline as described in [Section 5.1](#) (main outcomes for objective 2) will be summarized descriptively for all eligible patients in Cohort A and by treatment in Cohort B.

Concomitant disease and concomitant therapies will be summarized for all eligible patients in Cohort A and by treatment in Cohort B.

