6.2 IMPORTANT PROTOCOL VIOLATIONS

Patients with important protocol violations (IPVs) will be documented. The following list of IPVs will be used. Additional IPVs may be defined during the course of the study. Those will be assessed during the Medical and Quality Review meetings (MQRM); if the list of IPVs needs to be enlarged, it will be documented in the report planning meeting minutes before database lock.

Table 6.2: 1 Important protocol violations

Category / Code	Description	Requirements	Excluded from
A	Entrance criteria not met		
A1	Inclusion criteria not met		
A1.1	Informed consent not given	Date of written informed consent missing	All
A1.2	Informed consent given too late	Date of written informed consent after date of baseline visit, date of first dose taken, or PACT-Q date	All

Table 6.2: 1 (continued) Important protocol violations

Category / Code	Description	Requirements	Excluded from
A1.3	Age < 18 years		All
A1.4	No diagnosis of non-valvular atrial fibrillation (NVAF)	For Cohort A, no existing diagnosis of NVAF, or for Cohort B, no new diagnosis of NVAF	All
A1.5	< 3 months of continuous VKA treatment for stroke prevention prior to baseline assessment	For Cohort A only, less than 3 months of continuous VKA treatment for stroke prevention prior to baseline assessment	All
A1.6	Previous treatment for stroke prevention	For Cohort B only, patients had previous treatment (i.e. used an oral anticoagulant within 1 year prior to enrolment) for stroke prevention	All
A1.7	IC prior to site initiation visit	Date of written informed consent prior to site initiation	All
A2	Exclusion criteria violated		
A2.1	Contraindication to the use of Pradaxa® or VKA		All
A2.2	Pradaxa® or VKA used for any other conditions	Patients receiving Pradaxa® or VKA for any other condition than stroke prevention in atrial fibrillation	All
A2.3	Participating in other clinical trial	Current participation in any clinical trial of a drug or device	All
A2.4	Participating in a Registry on the use of oral anticoagulation in AF	Current participation in a Registry, e.g. the Gloria registry program, on the use of oral anticoagulation in AF	All
Z	Other		
Z1	Patients on Pradaxa with CrCl < 30 ml/min		All

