6.3 PATIENT SETS ANALYSED

The main analysis population will consist of all eligible patients [i.e. all patients who took the prescribed treatment and without an important protocol violation (see [Table 6.2: 1](#))] from all participating countries.

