7.9.2 Laboratory data

Creatinine clearance is calculated in the eCRF according to Cockcroft-Gault formula at each visit and will be summarized descriptively. No additional laboratory data is collected systematically.

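### The SAP removes patients with creatinine clearance below 30 mL/min only if they take Pradaxa, and the Cohort B propensity model merges that range with 30 to <50; whether VKA patients below 30 stay in the comparison is not settled

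*SAP*

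**What the plan says.** Four parts of the SAP bear on this.

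- **Who is removed.** Table 6.2: 1 lists violation Z1 under the category for other violations: "Patients on Pradaxa with CrCl < 30 ml/min". The patients are excluded from all analyses. The requirements cell is empty, so no visit is named. No violation names VKA patients with low CrCl.
- **A possible second route.** The same table lists A2.1 under violated exclusion criteria: "Contraindication to the use of Pradaxa® or VKA". It mirrors exclusion criterion 1 in protocol section 9.2.2.1, which refers to the approved country label. Neither gives a CrCl limit, and neither says whether a contraindication to one drug removes a patient who takes the other.
- **The analysis set.** Section 6.3 defines it as "all patients who took the prescribed treatment and without an important protocol violation", so both rules feed into the Cohort B comparison.
- **The model and the matching.** Section 7.6 enters CrCl as "Creatinine clearance at baseline (<30 and 30 to < 50 combined", followed by 50 to <80, 80 or more, and not available. Patients are then matched on the score alone, by a "nearest neighbour matching algorithm with a caliper width of 0.05 and without replacement".

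On timing, section 7.9.2 says that "Creatinine clearance is calculated in the eCRF according to Cockcroft-Gault formula at each visit". Footnote 3 of the protocol's visit schedule limits this to visits where a serum creatinine result already exists. Section 6.7 says that "Baseline values are the values collected at baseline visit (Visit 1").

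**The concern.** Z1 makes entry to the Cohort B comparison depend on treatment received: at the same low CrCl, a Pradaxa patient leaves and a VKA patient is not named. A propensity model balances covariates among the patients who are in the set. It cannot repair a restriction applied to one arm only, and here the merged level also hides the difference.

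If VKA patients below 30 do remain, the matched VKA group includes a range of renal function that has been cut out by rule from the Pradaxa group. If that range goes with different PACT-Q2 scores, the matched mean difference carries part of that gap as well as any treatment difference. The by-treatment description of kidney function, a main outcome for objective 2, would be cut in the same one-sided way.

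The missing visit in Z1 is a smaller matter. CrCl can be available at three visits, so Z1 could be applied to the baseline value or to any value.

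**Working it through.** **Does the consequence follow from the text?**

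1. After Z1, no Pradaxa patient with a known baseline CrCl below 30 is in the set.
2. Suppose A2.1 does not remove VKA patients below 30. Take one of them and a Pradaxa patient at 30 to <50 who has the same level on every other covariate.
3. Both sit in the merged CrCl level, so their covariate vectors and fitted scores are identical. The score difference is 0, inside the 0.05 caliper, and the pair is allowed.
4. The post-matching baseline summary in section 7.6 might show the imbalance, but no action is tied to it.

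**The plan's own power figure.** Protocol section 9.5 gives 1192 Cohort B patients, 30% loss to follow-up and matching, two-sided alpha 0.05, a standardized difference of 0.14 and power over 80%.

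- Pairs: 1192 × 0.70 / 2 = 417.
- Paired t-test power at 0.14: 81.4%. The stated figure reproduces.
- A two-sample calculation with 417 per group gives 52.5%, so 0.14 has to be read on the standard deviation (SD) of the paired difference.
- With the SD of 16 in section 9.5, the design difference is 0.14 × 16 = 2.24 points. If matched pairs were uncorrelated, the SD of differences would be 16 × √2 = 22.6, and the design difference 0.14 × 22.6 = 3.16 points.

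**Illustrative size.** Shift in the matched mean difference = q × g. Here q is the share of matched sets whose VKA patient is below 30, and g is the mean PACT-Q2 gap between VKA patients below 30 and those at 30 to <50. The documents give neither, so both are assumptions. The gaps below are 0.2 and 0.5 of the SD of 16.

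| q | g (points) | Shift (points) | Share of 2.24 |
|---|---|---|---|
| 1% | 3.2 | 0.03 | 1% |
| 5% | 3.2 | 0.16 | 7% |
| 5% | 8 | 0.40 | 18% |
| 10% | 8 | 0.80 | 36% |

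For the second row, the standard error is 16/√417 = 0.78, so the shift is 0.16/0.78 = 0.2 standard errors. A nominal 5% two-sided error rate becomes about 5.5%, or 5.2% if the SD of differences is 22.6.

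**Cost of restricting both groups.** Assume each VKA patient removed costs one matched pair. This is an upper bound, since a freed Pradaxa patient may be matched elsewhere.

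| Pairs lost | Pairs left | Power at 0.14 |
|---|---|---|
| 0% | 417 | 81.4% |
| 2% | 408 | 80.5% |
| 5% | 396 | 79.4% |

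Power stays at or above 80% down to 403 pairs.

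**The case against.** The strongest reply is A2.1. Read literally, a contraindication to either drug excludes the patient whichever drug is taken. If the country labels set a renal limit at 30, VKA patients below it are already out and no bias arises. The labels are not in the documents, so this reply can be neither confirmed nor dismissed. The existence of Z1 as a separate item, outside the exclusion-criteria block, suggests that A2.1 was not relied on, but Z1 could equally be a data-based check on an investigator's judgement. The <30 wording in the covariate is weak evidence, because an empty or sparse level is often folded into its neighbour.

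A reader might infer that VKA patients below 30 have no Pradaxa counterparts at all. The documents do not support that. Pradaxa patients with no creatinine value stay in under the not-available level, and some may be below 30. Age and HAS-BLED, which counts abnormal renal function, are also in the model, so not every VKA patient below 30 will share a profile with a Pradaxa patient at 30 to <50.

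A reader might also take the top of the assumed range, 10% and 8 points, as a forecast. With a standard error of 0.78 it would put the error rate at 17.5%, but it stacks two extremes that nothing in the documents supports. No PACT-Q2 item asks about kidney function, and the only between-drug differences quoted in protocol section 9.5 are -0.6 and 1.1 points.

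What stands after this is that the rule as written differs by treatment, and the SAP does not say whether another rule removes the difference.

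**Conclusion.** The point holds as a conditional one. Z1 is limited to Pradaxa patients, and the merged level lets VKA patients below 30 be matched to Pradaxa patients at 30 to <50. This matters only if A2.1 does not already remove those VKA patients. The documents show an unresolved rule; they do not show a biased comparison.

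If there is a bias, it is probably small and its direction is unknown. The 0.16-point illustration rests on an assumed share of 5%, an assumed gap of 3.2 points, and an SD of 16; no estimate can be drawn from the documents.

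Nor do the documents support reading Z1 as removing Pradaxa patients on post-baseline values. The other listed violations concern consent or entry, so baseline is the likelier meaning, and naming the visit is a clarification only.

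Priority is low: section 7.6 states that "confidence intervals and p-values from statistical models are used for exploratory purposes".

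**What to change.** The change concerns the analysis set only; it is not a statement about whom to treat or with what.

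1. Reconcile A2.1, Z1 and the <30 part of the covariate level, and state whether A2.1 removes VKA patients with CrCl below 30.
2. If it does not, apply the same baseline CrCl restriction, at the cut-off that Z1 already uses, to both treatment groups in the Cohort B comparison before fitting the propensity model.
3. State in Table 6.2: 1 that Z1 is judged on the Visit 1 value.

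Splitting the merged level would not be a substitute. With Pradaxa patients below 30 removed by Z1, a separate level would hold only VKA patients, and the logistic model could not estimate its effect.

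The cost is a few lines in Table 6.2: 1 and section 7.6. The data are already in the eCRF, and section 6.2 allows the violation list to be enlarged before database lock. If step 2 is needed, a few VKA patients leave, and nominal power can slip just under 80% if more than about 3.4% of pairs go ((417 − 403)/417). Patients with no baseline creatinine cannot be screened in either group, and the report should say so.

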7.8 EXPOSURE TIME

The exposure will be summarized descriptively for all eligible patients in Cohort A, by treatment in Cohort B, and total.

Exposure time [days] = date of last administration of Pradaxa or VKA – date of Pradaxa or VKA administration + 1 day. In case of death, the treatment stop date will be imputed as the earlier of (date of last administration of Pradaxa or VKA, date of death). Any temporary discontinuation is included in the exposure time.

7.9 SAFETY ANALYSIS

Safety analyses will be performed separately for Cohort A and B and by treatment for Cohort B, and will include all eligible patients. Statistical analysis and reporting of safety parameters will be descriptive in nature; and will be based on BI standards. No hypothesis testing is planned.

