9.2.2 Study population

9.2.2.1 Inclusion Criteria

Cohort A:

- 1A. Written informed consent prior to participation
- 2A. Female and male patient's ≥ 18 years of age with a diagnosis of non-valvular atrial fibrillation.
- 3A. At least 3 months of continuous VKA treatment for stroke prevention prior to baseline assessment.
- 4A. Patients switched to Pradaxa[®] according approved country label and physician's discretion.

OR

Cohort B:

- 1B. Written informed consent prior to participation.
- 2B. Female and male patients ≥ 18 years of age newly diagnosed with non-valvular atrial fibrillation and no previous treatment for stroke prevention (no use of any OAC within one year prior to enrolment).
- 3B. Stroke prevention treatment initiated with Pradaxa[®] or VKA according to approved country label and physician's discretion.

Exclusion Criteria

1. Contraindication to the use of Pradaxa[®] or VKA as described in the approved country label

2. Patients receiving Pradaxa[®] or VKA for any other condition than stroke prevention in atrial fibrillation.
3. Current participation in any clinical trial of a drug or device
4. Current participation in a Registry, e.g. the Gloria registry program, on the use of oral anticoagulation in AF

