9.7.2 Planned Analysis

Analyses will be performed by Boehringer Ingelheim or Boehringer Ingelheim's designees. The main analysis population will consist of all eligible patients (i.e. all patients fulfilling all inclusion criteria and no exclusion criteria) from all participating countries.

Summary statistics for continuous variables will include the N, mean, standard deviation, minimum, Q1 (lower quartile), median, Q2 (upper quartile), and maximum value; tabulations of categorical variables will present all possible categories and will display the number of observations per category as well as percentages. Estimates will be presented with 95% confidence intervals.

Additional details of the planned analysis will be provided in the statistical and epidemiological analysis plan (SEAP).

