9.7.5 Safety Analyses

Safety analyses will be performed separately for Cohort A and B, and will include all enrolled patients with an actual follow-up. Statistical analysis and reporting of AEs will be descriptive in nature, will be based on BI standards, and will focus on adverse drug reactions (ADRs) to Pradaxa[®] and VKA. No hypothesis testing is planned.

Occurrences of ADRs will be analyzed relative to the number of patients treated as well as observed person-years (i.e. time at risk). Safety analysis will be based on the concept of treatment emergent ADRs. Patients will be analyzed according to the anticoagulation treatment received at the time of the event. If no concurrent anticoagulation treatment is administered, then events occurring within a washout period of 3 days (for Pradaxa[®]) or 6 days (for VKA) after discontinuation of anticoagulation treatment will be assigned to the last treatment given. This washout period will also be included as time at risk for derivation of total person-years. ADRs that deteriorate under treatment will also be considered as “treatment emergent”. Events occurring prior to first intake of anticoagulation treatment prescribed at baseline, during periods without any anticoagulation treatment (excluding washout periods), or after the end of the 6 month follow-up (excluding washout periods) will not be considered treatment emergent events and will not be included in the summary tables.

The following parameters will be included in the safety analyses:

- Adverse drug reactions
- Adverse drug reactions leading to discontinuation of anticoagulation treatment
- Serious adverse drug reactions
- Adverse events leading to deaths

Schedule of Planned Analyses

No interim analysis is planned for Cohort A.

For Cohort B, it is planned that an interim analysis that assesses the comparability of patients in the Pradaxa[®] and VKA groups based on propensity scores will be performed when approximately half of the target sample size is reached (see details in Section 9.7.2.1).

For each cohort, the final analyses as specified in Section 9.7.2 will be performed once the data collection is completed, the data sets are cleaned, and the database is locked for that cohort. The final analysis for both cohorts may be performed together, if their complete data becomes available at the same time. One final report will be prepared at the completion of both cohorts.

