4. CHANGES IN THE PLANNED ANALYSIS OF THE STUDY

4.1 SUMMARY OF CHANGES TO THE STUDY

Patient analysis set has been updated to include all patients who took the prescribed treatment and without an important protocol violation.

For Cohort B, no formal interim analysis will be performed; instead a preliminary analysis will be performed to assess the comparability of the matched Pradaxa[®] and VKA patients based on propensity scores matching analysis when approximately half of the target sample size is reached.

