7.9.1 Adverse events / adverse drug reactions

Reporting of adverse events (AEs) in this study will focus on serious and non-serious adverse drug reactions (ADRs) to Pradaxa[®] and VKA, fatal AEs and pregnancies. All analyses of ADRs and fatal AEs will be based on the number of patients with ADRs and fatal AEs and NOT on the number of ADRs and fatal AEs.

For analysis multiple AE occurrence data in the eCRF will be collapsed into an AE provided that all of the following applies:

- All AE attributes are identical (lowest level term, intensity, action taken, therapy required, seriousness, reason for seriousness, relationship, outcome).
- The occurrences were time-overlapping or time-adjacent (time-adjacency of 2 occurrences is given if the second occurrence started on the same day or on the day after the end of the first occurrence).

For further details on summarization of AE data, please refer to [\(4, 6\)](#).

Occurrences of AEs will be analysed relative to the number of patients treated as well as observed person-years (i.e. time at risk). Analysis of AEs will be based on the concept of treatment emergent AEs. Patients will be analysed according to the anticoagulation treatment received at the onset of the AE. If no concurrent anticoagulation treatment is administered, then AEs occurring within a washout period of 3 days (for Pradaxa[®]) or 6 days (for VKA) after discontinuation of anticoagulation treatment will be assigned to the last treatment given. This washout period will also be included as time at risk for derivation of total person-years. AEs that deteriorate under treatment will also be considered as “treatment emergent”. Events occurring prior to first intake of anticoagulation treatment prescribed at baseline, during periods without any anticoagulation treatment (excluding washout periods), or after the end of the 6 month follow-up (excluding washout periods) will not be considered treatment emergent AEs and will not be included in the summary tables.

According to ICH E3 [\(7\)](#), AEs classified as ‘other significant’ needs to be reported and will include those non-serious AEs with

- (i) ‘action taken = discontinued’ or ‘action taken = reduced’, or
- (ii) marked haematological and other lab abnormalities or lead to significant concomitant therapy as identified by the Clinical Monitor/Investigator at a Medical Quality Review Meeting.

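### SAP 7.9 leaves treated patients with an important protocol violation out of the safety tables, which departs from protocol 9.7.5 without a stated reason

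*SAP*

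**What the plan says.** The protocol keeps two populations. Section 9.7.2 defines the main analysis population as eligible patients, meaning "all patients fulfilling all inclusion criteria and no exclusion criteria". Section 9.7.5 gives safety its own, wider population: it "will include all enrolled patients with an actual follow-up", with no filter for protocol violations.

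The SAP uses one population for both purposes. Section 7.9 says the safety analyses are done separately for the two cohorts "and by treatment for Cohort B, and will include all eligible patients". Section 6.3 defines eligible as "all patients who took the prescribed treatment and without an important protocol violation".

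The change is disclosed in two places. SAP 4.1 records: "Patient analysis set has been updated to include all patients who took the prescribed treatment and without an important protocol violation". That entry does not mention safety. The history table entry for the 02-JAN-18 revision does list the safety population among the updates. Neither entry gives a reason.

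In SAP Table 6.2: 1 the exclusion column reads All in every row. The rows include A2.1 (contraindication to Pradaxa or VKA) and Z1, "Patients on Pradaxa with CrCl < 30 ml/min". SAP 6.2 also allows further IPVs to be added before database lock.

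**The concern.** Removing ineligible patients can be sensible for a questionnaire comparison, where the aim is to describe a defined population. It does not carry over to safety. A patient who took the drug despite a contraindication, or who turns out to have had earlier anticoagulation, was still exposed, and a reaction in that patient is still an observation of this study.

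At stake is the completeness of the reported ADR and fatal adverse event summary by treatment. Followed as written, the SAP omits events in treated IPV patients whatever their risk. If their risk differs from that of the others, the tabulated frequencies no longer describe the treated patients as a whole.

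**Working it through.** **1. Count the rows of Table 6.2: 1.** A1.1 to A1.7 give 7, A2.1 to A2.4 give 4, and Z1 gives 1: 7 + 4 + 1 = 12. Three rows concern consent (A1.1 missing, A1.2 too late, A1.7 before site initiation). That leaves 12 − 3 = 9 rows on diagnosis, age, previous treatment, contraindication, other indication, other studies and creatinine clearance.

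**2. Follow one patient through both documents.** Take a consented, treated and followed Cohort B patient who meets A2.1 and has an ADR between Visits 2 and 3.
- Protocol 11.2: the ADR is collected, because collection runs from consent to the end of the study with no exception for violations. On Pradaxa it is also reported on the expedited timelines.
- Protocol 9.7.5: the patient is enrolled and followed, so the ADR is tabulated.
- SAP 6.2, 6.3 and 7.9: the patient has an IPV, so is not eligible and is not in the safety analyses.
- SAP 7.9.1: the tables described there come under the 7.9 population. The only listing mentioned is for pregnancies. The ADR appears in no table.

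**3. Compare the two sets exactly.** The SAP set is narrower because of the IPV filter and the treated requirement. It is wider in one respect: it does not carry over the protocol's condition of an actual follow-up. It is therefore not a strict subset of the protocol set.

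**4. Scale, on assumed inputs.** There is no figure in the plan to reproduce. Let f be the share of a treatment group removed for IPVs, p the ADR risk in those kept, and kp the risk in those removed.
- All-treated frequency = (1 − f)p + f·kp = p[1 + f(k − 1)].
- Tabulated frequency = p.
- Tabulated ÷ all-treated = 1 / [1 + f(k − 1)].

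| f (assumed) | k = 0.5 | k = 1 | k = 2 |
|---|---|---|---|
| 2% | 1/0.990 = 1.010 | 1.000 | 1/1.02 = 0.980 |
| 5% | 1/0.975 = 1.026 | 1.000 | 1/1.05 = 0.952 |
| 10% | 1/0.950 = 1.053 | 1.000 | 1/1.10 = 0.909 |

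**5. Events missing even without bias.** Protocol 9.5 plans 1192 Cohort B patients in a 1:1 ratio, so 1192/2 = 596 per treatment; Cohort A has 598. At f = 5%, 596 × 0.05 = 29.8 patients leave one Cohort B group. With an assumed ADR risk of 2%, 5% or 10% among them, 0.6, 1.5 or 3.0 patients with an ADR would be expected to go untabulated.

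**6. Row Z1.** It names no visit, although protocol Table 9.2.2.3: 1 and SAP 7.9.2 provide for creatinine clearance at each visit where a creatinine value already exists. Read literally, a follow-up value could remove a patient who is already exposed. The protocol's criterion on contraindications is framed only "as described in the approved country label", and the labels are not in the documents, so whether Z1 restates an entry criterion or adds one cannot be settled from the text.

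**The case against.** The case for leaving the SAP alone has several parts.

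- *The change is disclosed.* True: this is not concealment. But a log entry is not a reason.
- *Restriction to eligible patients fits the protocol's aims.* Section 9.8 wants the analysed population to match the protocol-described one. That supports the main analysis set; it does not override the separate safety set in 9.7.5.
- *The visible SAP may be incomplete.* The contents list skips 6.4, 7.7 and 9, and adverse event reporting defers to company standards that are not available here. This stands as a limit: the absence of a wider safety table can be asserted only for the available text. The population sentence in 7.9 is explicit all the same.
- *Impact is small.* Safety is descriptive, is not a study objective and involves no test. This bears on priority, not on whether the departure exists.
- *The line on consent is a judgement.* Patients under A1.2 or A1.7 may also have been exposed. This stands; leaving them out rests on permission to use their data, not on exposure.

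A reader might also infer that SAP 7.9 contradicts 7.9.1, which says "Occurrences of AEs will be analysed relative to the number of patients treated as well as observed person-years". The documents do not support that. Section 7.9 sets the population and 7.9.1 the denominator, and patients treated can mean those treated within the eligible set.

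**Conclusion.** The departure is real and should be fixed. The SAP replaces the protocol's safety population with one filtered on IPVs, gives no reason, and so leaves events in treated patients with a non-consent IPV out of the safety tables in the available text. The omission follows from the wording and needs no assumption.

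The consequences for the frequencies do rest on assumptions, because neither the IPV share nor ADR risks are given. At 5% removed, the tabulated frequency would be 1.03, 1.00 or 0.95 of the all-treated one for half, equal or double risk. Neither size nor direction can be stated.

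Three stronger readings are not supported:
- *That exposed patients in general are missing.* Only those with an IPV are; the other treated patients are tabulated.
- *That the filter tilts the Pradaxa versus VKA comparison.* Z1 is the only row worded for Pradaxa patients alone. The other rows that apply in Cohort B are not limited to one treatment, and how A2.1 falls depends on labels not in the documents. A between-treatment ratio built on Pradaxa-only removals would have no basis.
- *That results drove the change.* The revision is dated 02-JAN-18, close to the planned end of data collection on 11 January 2018, but nothing shows that results played a part.

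**What to change.** - Base the safety tables, or at least a supplementary set of them, on all validly consented patients who took at least one dose of the prescribed anticoagulant, by treatment received. Ignore IPVs other than the consent rows A1.1, A1.2 and A1.7.
- Do not exclude treated patients for lack of a follow-up visit, since that would remove patients the SAP now keeps.
- Keep the IPV exclusions for the PACT-Q2 analyses.
- Give the reason for any remaining departure from protocol 9.7.5.
- Separately, state which visit's creatinine clearance triggers Z1, and reconcile Z1 with the protocol's entry criteria.

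The cost is SAP wording and one more population flag; the data are already collected. The downside is that the safety and PACT-Q2 tables will have different Ns, which a footnote can explain.
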